| Number of families ⁶⁰ | Intervention: 361 Control: 199 Total: 560 |
| Number of participants | Intervention: 369 adults, 193 children Control: 203 adults, 101 children Total: 572 adults, 294 children |

⁶⁰ Final numbers reported (post attrition) that we will be analysing, rather than in the entire sample.

Updated sampling calculation (LAs = 10) – Only SF sample and latest assumptions

[figure not shown]

Figure 3 – Sampling calculations

SF Sample Size Calculation Table

| | |
|--------------------------------|------------|
| MDES | 0.446 |
| Alpha Level (α) | 0.05 |
| Two-tailed or One-tailed Test? | Two-tailed |
| Power (1- β) | 0.8 |
| Baseline/Endline correlations | |
| Individuals | 0.6 |
| Families | 0.6 |
| Local authorities | 0.6 |
| Average cluster size | |
| Individuals in families | 1.5 |
| Families in local authorities | 56 |
| Number of local authorities | 10 |
| Intraclass cluster correlation | |
| Families | 0.3 |
| Local authorities | 0.1 |

Assumptions

- 3 level clustering – individual in family in local authority
- Assumed a low ICC for families in terms of family functioning (expect different views)
- Assumed a very low ICC for local authorities in terms of family functioning (some clustering of scores based on shared factors, but not strong)
- Assumed baseline/endline correlations of 0.6 at all levels (unknown)

Figure 4 – SF Sample size calculation table

Outcome measures

Table 3: Primary outcome measures

| Variable | Progress towards personal goals |
|------------|--|
| Measure | Goal Based Outcomes (GBO) ⁶¹ |
| Sample | Parents/carers and children/young people aged 8 and over. The GBO will be administered as part of the Family Outcome Questionnaire at an individual level by keyworkers. There will be an adult version (for use with adults and young people aged over 12) and a child-friendly version (for use with children aged 8 to 12). Total GBO scores will be reported, as well as themed scores. We anticipate theming goals using existing taxonomies from psychotherapy research ^{62,63} and using inductive analysis owing to the novel context for use of the GBO. |
| Time point | Baseline: within the assessment period of the first six weeks of the keyworker working with a family. Midline: at a review point when working with the family. Typically, this is between two to five months of working with the family. Endline: At closure when the keyworker stops working with a family. |

Secondary outcome measures for families:

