In line with the pilot's theory of change of creating systemic practice supporting families to make meaningful progress towards personal goals, the Goal-Based Outcome (GBO) has been chosen in consultation with the expert working group.⁶⁴ The GBO tool is a way of evaluating progress towards goals in work with children, young people, and their parents and carers. The GBO assesses how far an individual feels they have moved towards reaching a goal that they have set for themselves at the beginning of their support, on a scale between 0 and 10. The measure suggests setting three goals. GBOs are also a tool to facilitate shared decision making and enable more personalised support.⁶⁵ The Family Outcome Questionnaire which includes the GBO questions are included in Annex B.

As the GBO tool is an idiographic outcome measure, the approach to testing psychometric properties differs from traditional measures. An assessment of the GBO's psychometric properties is as follows:

- **Internal consistency** (the degree to which similar items within a scale correlate with each other): There are mixed views on whether internal consistency of goal measures is relevant, given that the goals set may be focussed on the different

⁶⁴ For more information please see: [The Goal-Based Outcome \(GBO\) Tool Guidance](https://www.goals-in-therapy.com/the-gbo-tool) PDF and the dedicated website: <https://www.goals-in-therapy.com/the-gbo-tool>

⁶⁵ Law, D., & Jacob, J. (2015). Goals and Goal Based Outcomes (GBOs): Some useful information. Third Edition. London, UK: CAMHS Press)

areas of change. However, Edbrooke-Childs et al., found evidence of good internal consistency for parent rated goals.⁶⁶

- **Test-retest reliability** (the degree to which the same respondents have the same score after a period of time when goals shouldn't have changed): Acceptable stability over a 6 to 24 week period has been found.⁶⁷
- **Concurrent validity** (the correlation of the measure with others measuring the same concept): Parent and young person reported goals have been found to be significantly moderately correlated with measures of functioning and satisfaction. Using multilevel analysis techniques, moderate convergent validity has been found with measures of wellbeing, self-esteem and depression.

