- **Discriminant validity** (the Lack of correlation with opposite concepts): No significant correlations have been found between parent or young person reported GBO and other measures of symptoms.^{68 69} This suggests that goals may capture areas of change not explored by these symptom measures.⁷⁰

The suggested 'meaningful change' level for GBO, based on the principles of the reliable change index, is reported to be 2.45 in a 1-10 scale.⁷¹ As noted earlier, studies using the GBO show large effect sizes ranging from 1.33 to 2.37 (see section on power calculations for references). As this is the first time (to our knowledge) that the GBO is being used in the context of children's social care, this is relatively exploratory, but we hope to see similar effect sizes to this range to demonstrate evidence of promise. We intend to report overall GBO scores across all goals, as well as for themed goals. Goals will be themed using existing taxonomies from psychotherapy research^{72,73}. However, given that this is the first time, to our knowledge, that the GBO is being used in a study of Early Help, we will also generate our own themes inductively from the data. The measure is licensed under creative commons (CC) and therefore, free to use for the delivery and improvement of health and/or social care. It is also currently available in 9 different languages.

⁶⁶ Edbrooke-Childs, J., Jacob, J., Law, D., Deighton, J., & Wolpert, M. (2015). Interpreting standardized and idiographic outcome measures in CAMHS: what does change mean and how does it relate to functioning and experience?. *Child and Adolescent Mental Health*. 20(3), 142-148. <https://doi.org/10.1111/camh.12107>

⁶⁷ Duncan, C., Cooper, M., & Saxon, D. (2022). Test-retest stability, convergent validity, and sensitivity to change for the Goal-Based Outcome tool for adolescents: Analysis of data from a randomized controlled trial. *Journal of Clinical Psychology*. <https://doi.org/10.1002/jclp.23422>

⁶⁸ Edbrooke-Childs, J., Jacob, J., Law, D., Deighton, J., & Wolpert, M. (2015). Interpreting standardized and idiographic outcome measures in CAMHS: what does change mean and how does it relate to functioning and experience?. *Child and Adolescent Mental Health*. 20(3), 142-148. <https://doi.org/10.1111/camh.12107>

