The questionnaire will ask a series of questions divided into three sections. They will cover:

- **Your family** – 15 questions about how you see your family at the moment.
- **Your goals** – goals (up to three) you want to achieve for your family through this service. It also asks your views on your current progress towards these goals.
- **Your keyworker** – 10 questions about your relationship with your keyworker.

If you have any questions when completing the questionnaire **please ask your keyworker and they will be able to help you.**

Section 1: Your Family

In this section we would like you to tell us about how you see your family at the moment. **So we are asking for your view of your family.** When people say 'your family' they often mean the people who live in your house. **But we want you to choose who you want to count as the family you are going to describe.**

There are 15 short questions. Please tick whether the statement describes your family very well through to not well at all. For example, if a statement was "We are always fighting each other" and you felt this was not especially true of your family, you would tick the box that says "Describes us: not well".

Very Well / Well/ / Partly / Not very well / Not at all

X

Do not think for too long about any question, but do try to tick one of the boxes for each question.

For each line, would you say **this describes our family**: Very well / Well / Partly / Not very well / Not at all / Do not want to answer

1. In my family we talk to each other about things which matter to us
2. People often don't tell each other the truth in my family
3. Each of us gets listened to in our family
4. It feels risky to disagree in our family
5. We find it hard to deal with everyday problems
6. We trust each other
7. It feels miserable in our family
8. When people in my family get angry they ignore each other on purpose
9. We seem to go from one crisis to another in my family
10. When one of us is upset they get looked after within the family
11. Things always seem to go wrong for my family

12. People in the family are nasty to each other
13. People in my family interfere too much in each other's lives
14. In my family we blame each other when things go wrong
15. We are good at finding new ways to deal with things that are difficult

Section 2: Your Goals

In this section we want to know the most important **goals** to you that you want to achieve for your family in coming to this service.

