We will ask you to list up to **three** of your goals. After each goal we will ask how close you feel you are currently in progress to reaching that goal on a scale from zero to ten. A score of zero means no progress has been made towards a goal, a score of ten means a goal has been reached fully, and a score of five is exactly half way between the two.

Your first goal is:

How close do you feel to reaching your first goal?

- 1 – Goal not at all met
- 2
- 3
- 4
- 5 – Half way to reaching goal
- 6
- 7
- 8
- 9
- 10 – Goal reached

Your second goal is:

How close do you feel to reaching your second goal?

- 1 – Goal not at all met
- 2
- 3
- 4
- 5 – Half way to reaching goal
- 6
- 7
- 8
- 9
- 10 – Goal reached

Your third goal is:

How close do you feel to reaching your third goal?

1 – Goal not at all met

2

3

4

5 – Half way to reaching goal

6

7

8

9

10 – Goal reached

Section 3: Your Keyworker

This section asks 10 questions about working with your keyworker present here today.

For this section, you **do not need to discuss** your answers with your keyworker. Instead, please give your honest opinion on the support you have been given. Please note, answers given here or anywhere in this questionnaire **will not affect the support you receive from this service** in any way.

For each line, would you say **this describes your relationship with your keyworker**:
Poor / Fair / Good / Very good / Excellent / Does not apply / Do not want to answer

1. **Making you feel at ease** (*introducing him/herself, explaining his/her position, being friendly and war towards you, treating you with respect, not cold or abrupt*)
2. **Letting you tell your "story"** (*giving you time to fully describe your condition in your own words; not interrupting, rushing, or diverting you*)
3. **Really listening** (*paying close attention to what you were saying; not looking at the notes or computer as you were talking*)
4. **Being interested in you as a whole person** (*asking/knowing relevant details about your life or your situation; not treating you as 'just a number'*)
5. **Fully understanding your concerns** (*communicating that he/she had accurately understood your concerns and anxieties; not overlooking or dismissing anything*)
6. **Showing care and compassion** (*seeming genuinely concerned, connecting with you on a human level; not being indifferent or 'detached'*)

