In this section we want to know the most important **goals** to you that you want to achieve for your family in coming to this service.

We will ask you to list up to **three** of your goals. After each goal we will ask how close you feel you are currently in progress to reaching that goal on a scale from zero to ten. A score of zero means no progress has been made towards a goal, a score of ten means a goal has been reached fully, and a score of five is exactly half way between the two.

In coming to our service today, what are some of the goals you want to achieve?

Goal 1

Our Goal is:

.....
Made by:

How close are you to reaching this goal?

0 1 2 3 4 5 6 7 8 9 10

Not at all close

Halfway

Goal reached!

Goal 2

Our Goal is:

.....
Made by:

How close are you to reaching this goal?

0 1 2 3 4 5 6 7 8 9 10

Not at all close

Halfway

Goal reached!

Goal 3

Our Goal is:

.....
Made by:

How close are you to reaching this goal?

0 1 2 3 4 5 6 7 8 9 10

Not at all close

[figure not shown]
[figure not shown]
[figure not shown]
[figure not shown]
[figure not shown]
[figure not shown]
Halfway

[figure not shown]
[figure not shown]
Goal reached!

Section 3: Your Keyworker

This section asks 10 questions about working with your keyworker present here today.

For this section, you **do not need to discuss** your answers with your keyworker. Instead, please give your honest opinion on the support you have been given. Please note, answers given here or anywhere in this questionnaire **will not affect the support you receive from this service** in any way.

| | | | | | | |
|---|---|---|--|---|---|---|
|  | 1... making you feel at ease? (being friendly and warm towards you) | | | | | |
| | poor | fair | good | very good | excellent | does not apply |
| |  |  |  |  |  |  |
|  | 2... letting you tell your 'story'? (giving you time to fully describe things in your own words) | | | | | |
| | poor | fair | good | very good | excellent | does not apply |
| |  |  |  |  |  |  |
|  | 3... really listening? (paying close attention to what you are saying) | | | | | |
| | poor | fair | good | very good | excellent | does not apply |
| |  |  |  |  |  |  |
|  | 4... being interested in you as a whole person? (asking/knowing relevant details about your life, your situation) | | | | | |
| | poor | fair | good | very good | excellent | does not apply |
| |  |  |  |  |  |  |

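### The primary outcome forms disagree on the rating scale (1–10 for adults, 0–10 for children) and on who uses which form, so raw ratings are not on one metric

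*Protocol*

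**What the plan says.** The scale is described in four places in the protocol.

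- **Primary outcome measure section:** progress is rated "on a scale between 0 and 10".
- **Same section, meaningful-change benchmark:** it "is reported to be 2.45 in a 1-10 scale".
- **Annex B, adult questionnaire, Section 2:** the instruction gives a zero-to-ten scale and states "A score of zero means no progress has been made towards a goal". The printed options for all three goals then start at "1 – Goal not at all met" and run to 10.
- **Annex B, child questionnaire, Section 2:** the same instruction, with options "0 1 2 3 4 5 6 7 8 9 10".

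On who uses which form, Table 3 says "There will be an adult version (for use with adults and young people aged over 12"), with a child-friendly version for ages 8 to 12. Annex B heads the child form for ages 8 to 17. The adult form's respondent boxes cover parents, carers and other adults, with none for a referred young person.

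On scoring, respondents list "goals (up to three) you want to achieve for your family through this service". Table 3 says "Total GBO scores will be reported, as well as themed scores". The Primary outcome measure section speaks instead of overall scores across all goals. Neither place says sum or mean.

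On modelling, the Analysis section plans one three-level model for family outcomes, and Figure 4 gives the lowest level as individuals within families. SCORE-15 has a family composite (Table 4) and CARE scores are kept separate (Table 5). No such rule is given for the Goal Based Outcome.

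**The concern.** An adult who has made no progress is told that this is a zero and must then tick 1. A child in the same position ticks 0. Both ratings can enter the same model as if they meant the same thing. For ages 13–17 the scale depends on whether a keyworker follows Table 3 or Annex B.

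These are errors in the printed instrument for the primary outcome. They are not details left to a statistical analysis plan. They blur what a mean score or mean gain represents, and they leave unclear whose change can be judged against 2.45.

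Two further features of the form could matter, each on a condition.

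- **Number of goals.** If the total is a raw sum, a person with three goals scores higher than a person with one who made the same progress.
- **Identity of goals.** The protocol defines the measure as progress towards goals fixed when support began. The same forms, with blank goal boxes, serve first completion, review and closure, and the child form asks for the goals held on coming to the service that day. Nothing shown secures that the original goals are rated again.

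Either could differ by arm. The Study aims section lists goal-based outcomes among the systemic tools, and systemic practitioners, who support the use of outcome measures, are hired only in intervention authorities.

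**Working it through.** **Inputs.** Table 2 gives 369 adults and 193 children (intervention), and 203 adults and 101 children (control). The totals agree: 369 + 203 = 572 adults and 193 + 101 = 294 children. The response options come from Annex B and the 2.45 from the Primary outcome measure section. The planned minimum detectable effect of 0.446 is in standard deviation units and does not bear on this point.

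**1. The two scales side by side**

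| | Adult form | Child form |
|---|---|---|
| Instruction | 0–10 | 0–10 |
| Printed options | 1–10 | 0–10 |
| No progress | 1 | 0 |
| Half way | 5 | 5 |
| Goal reached | 10 | 10 |
| Range | 9 | 10 |

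The labels agree at 5 and 10 and differ only at the bottom. By position in the range, half way is (5 − 1)/9 = 0.44 on the adult form and 5/10 = 0.50 on the child form.

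**2. Effect on the arm contrast at the planned mix.** Assume that all adults use the adult form and all children the child form. The offset is at most 1 point, at the floor.

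- Adult share, intervention: 369/562 = 65.7%
- Adult share, control: 203/304 = 66.8%
- Difference: 1.1 percentage points × 1 point = 0.011 points per goal, or 0.03 on a sum of three goals

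**3. If form use differs by arm.** Let f be the share of children aged 13–17. The protocol does not give f, so it is an assumption. Suppose one arm follows Table 3 and the other Annex B. The difference in adult-form share, multiplied by the 1-point offset, bounds the shift.

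- Intervention follows Table 3: (369 + 193f)/562 − 203/304 = −0.011 + 0.343f. For f = 0.25, 0.50 and 0.75 this gives 0.07, 0.16 and 0.25 points.
- Control follows Table 3: 369/562 − (203 + 101f)/304 = −0.011 − 0.332f. This gives −0.09, −0.18 and −0.26 points.

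These are upper bounds, since they place every rating at the floor and ignore baseline adjustment.

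**4. The benchmark.** 2.45/9 = 27.2% of a 1–10 range, and 2.45/10 = 24.5% of a 0–10 range. Scaled by range, 2.45 on 1–10 would become 2.45 × 10/9 = 2.72 on 0–10. The same number is therefore a different fraction of each form.

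**5. Conditional: total as a raw sum.** The possible ranges are 1–10, 2–20 or 3–30 on the adult form and 0–10, 0–20 or 0–30 on the child form, for one, two or three goals. Assume a mean change of 3 points per goal in both arms. An arm difference of 0.1, 0.25 or 0.5 in the mean number of goals would then add 0.3, 0.75 or 1.5 points to the contrast in summed change with no extra progress. On the mean over goals, this source disappears.

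**The case against.** Several stronger readings are tempting, and the protocol does not support them.

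- **That scores are not comparable, so the trial's comparison fails.** The offset is present in both arms, the planned adult shares are nearly equal, and the upper two labelled anchors match. What stands is that raw adult and child ratings are not on one metric.
- **That goals are summed.** Table 3 sets the total against themed scores, the later text speaks of an overall score, and one benchmark study cited under Sample size calculations averaged three goals. The scoring rule may properly sit in the statistical analysis plan, so the goal-count risk is only conditional.
- **That follow-up ratings concern different goals.** A blank box can hold the original goal written in again. Keyworkers receive training and detailed guidance that is not shown. The risk is open but not established.
- **That form and goal count weaken the assumed baseline–endline correlation of 0.6.** A stable offset, or a goal count fixed at baseline, adds variance shared by both time points and tends to raise the correlation. Only re-set goals would lower it.
- **That the 1-point floor difference can be weighed against 2.45.** The latter is a threshold for change, and a respondent who stays on one form has the same floor each time.

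It is also fair to say that only paper versions are shown and the online form may differ. That does not remove the conflict, because paper answers are to be uploaded to the online survey.

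**Conclusion.** The point holds as an internal contradiction in the primary outcome instrument and should be corrected. The adult instruction disagrees with its own options and with the child form, the benchmark is on a different scale from the one in the body text, and the form for ages 13–17 is stated in two incompatible ways.

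Its effect on the planned arm contrast is about 0.01 points per goal, assuming that the Table 2 mix is achieved and that both arms assign forms in the same way. If they assign forms differently, the shift could reach roughly 0.1 to 0.3 points at the floor, depending on the unknown share of teenagers. The main harm is to interpretation of scores and use of the 2.45 benchmark. The goal-count and goal-identity risks rest on a scoring rule and keyworker guidance that are not shown.

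**What to change.** **In the forms and keyworker guidance**

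- Correct the adult instruction to match its printed 1–10 options. The timeline starts family data collection in January 2025, so changing the options part-way would mix scales within respondents.
- Reconcile Table 3 with Annex B on the form for ages 13–17, and keep each respondent on the same form and scale throughout.
- Copy the baseline goals onto the review and closure forms for rating, and list new goals separately.

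**In the analysis**

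- Define the primary score as the mean rating over the goals recorded at baseline.
- Include form version as a covariate, or standardise within form. Avoid converting adult ratings by (x − 1)/9, which puts adult half way at 0.44 against 0.50 for children.
- State the 2.45 benchmark on the scale actually used for each form.

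**For any full trial**, print one response scale on both forms. The pilot is meant to judge whether its measures are appropriate, so this belongs in its findings.

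The cost is a scoring rule, one covariate, a small wording edit and some extra guidance. Records already collected with re-set goals must be identified and flagged. The final statistical analysis plan is due before any analysis, so the scoring decisions can be fixed there.
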